12.1 Dosing Compliance

Dosing compliance (% compliance) will be assessed by calculating the number of doses taken and comparing that to the number of expected doses as follows:

Compliance (%) = _____ X 100% Number of Expected Doses

The number of actual doses taken will be recorded from the eCRF. The number of expected doses that will be used for calculating compliance will be calculated as follows:

- For subjects in dosing arms Q-Q: 4 x {[Date of Study Completion/Discontinuation Date of Visit 2 (Day 1)] + 1}, regardless of study completion status
- For subjects in dosing arms Q-B that discontinue prior to Visit 5 (Day 29): 4 x {[Date of Discontinuation Date of Visit 2 (Day 1)] + 1}
- For subjects in dosing arms Q-B that complete the study or discontinue on or after Visit 5 (Day 29): 4 x {[Date of Visit 5 (Day 29) Date of Visit 2 (Day 1)] + 1} + 2 x [Date of Study Completion/Discontinuation Date of Visit 5 (Day 29)]

For subjects who do not receive a dose of study drug per in office instillation, the number of expected doses will be 0 and compliance will be defined as 0.

A categorical dosing compliance variable will also be derived as non-compliant (<80%), compliant (\geq 80% and \leq 125%), and over compliant (>125%).

Dosing compliance (%) will be summarized with continuous descriptive statistics for each treatment arm, using the Safety population. The compliance category defined above will be summarized with discrete summary statistics.

A subject listing of dosing compliance and study drug accountability will also be produced.

A subject listing of run-in, run-in instillation, and run-in replacement will be provided as well as study drug assignment, instillation, and replacement.

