9.3.3 Visit 2: Day 1 -

- Study Run-in Collection
- Review of Inclusion/Exclusion Criteria
- Medical/medication history update
- AE query
- Multi-symptom Visual Analogue Scale (VAS)

- •
- BCVA Utilizing an ETDRS Chart
- Slit Lamp Biomicroscopy

• At least 15-minute wait between lissamine green staining and Schirmer's test

•	Run-in dosing 15-20 minutes
•	
•	Slit Lamp Biomicroscopy

- Review of Inclusion/Exclusion Criteria
- Randomization
- Study Drug Instillation at the Study Site: All subjects having a positive response (as defined above) and meeting all other screening eligibility criteria at the end of Visit 2 will be randomized to one of two treatment groups utilizing the IWRS system. Randomized subjects will self-administer their initial study drug dose bilaterally at the study site under supervision of a trained technician. Subjects will be instructed to dose four times a day (QID) in both eyes until their next visit.
- Study Drug Dispensation: Prior to discharge from the study site on Visit 2 (Day 1), randomized subjects will be educated on self-administration of study drug. Subjects will receive their assigned study drug kit with sufficient supply to last until Visit 3 and will be instructed NOT to self-administer study drug on the morning of their next scheduled study visit (Visit 3).

- AE Query
- Subjects will be scheduled for Visit 3.

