9.3.6 Visit 5 (Day 29 ± 2)

- Study Drug Collection
- Medical/medication history update
- AE query
- Multi-symptom Visual Analogue Scale (VAS)

- BCVA Utilizing an ETDRS Chart
- Slit Lamp Biomicroscopy

- Study Drug Dispensation: Prior to discharge from the study site on Visit 5, subjects will be assigned a new study drug kit(s) via the IWRS and will also be re-dispensed the remaining unused ampules from their previous kit for at-home dosing up to Visit 6. Depending on the assigned dosing regimen, subjects will be dispensed new kit(s) as follows:
 - Reproxalap/Placebo subjects in the all QID treatment regimen:
 - Subjects will continue to dose QID through the end of the treatment period
 - Subjects will be assigned two (2) kits at Visit 5
 - Reproxalap/Placebo subjects in the QID to BID treatment regimen:
 - Subjects will now be instructed to dose twice a day (BID) in each eye through the end of the treatment period
 - Subjects will be assigned one (1) kit at Visit 5
- Subjects will again be educated on self-administration of study drug. Subjects will be instructed to NOT self-administer study drug on the morning of their next scheduled study visit (Visit 6)
- AE Query
- Subjects will be scheduled for Visit 6.

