9.3.9 Visit 8 (Day 71 ± 3)

- Study Drug Collection
- Medical/medication history update
- AE query
- Multi-symptom Visual Analogue Scale (VAS)

• Study Drug Dispensation: Prior to discharge from the study site on Visit 8, subjects will be re-dispensed the remaining unused ampules from their previous kit for athome dosing up to Visit 9. Subjects will be reinstructed to dose BID or QID based on their assigned treatment regimen in both eyes until their next visit.

- Subjects will again be educated on self-administration of study drug. Subjects will be instructed to NOT self-administer study drug on the morning of their next scheduled study visit (Visit 9)
- AE Query
- Subjects will be scheduled for Visit 9.

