9.6.2 Discontinued Subjects

Subjects may be discontinued prior to their completion of the study due to:

- subject request/withdrawal
- AEs
- protocol violations
- administrative reasons (e.g., inability to continue, lost to follow up)
- Sponsor termination of study
- other

Note: In addition, any subject may be discontinued for any sound medical reason.

Notification of a subject discontinuation and the reason for discontinuation will be made to Ora and/or Sponsor and will be clearly documented on the eCRF.

9.7 **Study Termination**

The study may be stopped at any time by the investigator, the Sponsor, and/or Ora with appropriate notification.

9.8 **Study Duration**

An individual subject's participation will involve nine visits over approximately a 14week (~98 days) period (84 days of treatment and 14 days pre-screening).

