12.2 Treatment Exposure

Extent of treatment exposure for completed or discontinued subjects will be calculated in days using the following:

Extent of Exposure (days) = [Date of Study Completion/Discontinuation – Date of Visit 2 (Day 1)] + 1

Extent of treatment exposure for subjects who were lost to follow-up will be calculated in days using the following:

Extent of Exposure (days) = [Date of Last Recorded Visit – Date of Visit 2 (Day 1)] + 1

Extent of treatment exposure (days) for each subject exposed to study drug will be summarized with continuous descriptive statistics for each treatment arm, using the Safety population.

Subject listings of study drug exposure and dosing compliance will be produced.

13. Efficacy Analyses

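### The expected-dose formula in SAP 12.1 does not match the protocol's visit-day dosing instructions, so perfect adherence scores below 100%, and a fully adherent first-week leaver can be labelled non-compliant

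*SAP*

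**What the plan says.** SAP 12.1 defines compliance as doses taken divided by doses expected. Below 80% is non-compliant, 80% to 125% compliant, and above 125% over-compliant. Expected doses come from three lines:

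- Q-Q arms: "4 x {[Date of Study Completion/Discontinuation Date of Visit 2 (Day 1)] + 1}, regardless of study completion status". The minus sign between the two dates was lost when the PDF was read.
- "For subjects in dosing arms Q-B that discontinue prior to Visit 5 (Day 29"): the same expression, with the discontinuation date.
- Q-B subjects who complete, or who leave at or after Visit 5: four per day from Visit 2 to Visit 5 with both days counted, plus two per day after Visit 5 up to and including the exit date.

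A further rule reads: "For subjects who do not receive a dose of study drug per in office instillation, the number of expected doses will be 0", and compliance is then defined as 0.

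The protocol's dosing instructions around visits are these:

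- Day 1 (Protocol 9.3.3): "Randomized subjects will self-administer their initial study drug dose bilaterally at the study site", after the Visit 2 assessments and randomization. The SAP 3.2 schedule likewise places randomization and instillation in the post-exposure column.
- Every later visit: the morning dose is withheld. For the last one, subjects will "be instructed to NOT self-administer study drug on the morning of their next scheduled study visit (Visit 9").
- Visit 9 (Protocol 9.3.10): drug is collected and none is dispensed. Protocol 9.5 has ampules collected at every visit from Visit 2 to Visit 9.
- Visit 5, Q-B arms (Protocol 9.3.6): "Subjects will now be instructed to dose twice a day (BID) in each eye through the end of the treatment period".
- Protocol 9.8 gives the treatment period as "84 days of treatment and 14 days pre-screening".

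**The concern.** The denominator counts doses that the protocol's own instructions leave no room for. The exit day is charged four doses (two for a Q-B subject leaving after Visit 5), yet at a scheduled exit the morning dose is withheld and the drug is taken back. Day 29 is charged four doses in Q-B, although that morning's dose is withheld and BID starts at the visit. Day 1 is charged four, although the first dose comes at the end of a long visit.

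The error is a nearly fixed number of doses, so it weighs most on short stays. What is at stake is whether the compliance table can be read at face value: full adherence does not show as 100%, and someone who took every available dose in a short stay may be reported as non-compliant.

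**Working it through.** The documents print no expected-dose total or compliance rate, so there is no stated figure to reproduce. The check is a direct dose count.

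**Inputs.** The expected-dose lines and the 80% cut-off are from SAP 12.1. Visits are placed on their planned days: Visit 3 on Day 8, Visit 4 on Day 15, Visit 5 on Day 29 and Visit 9 on Day 85. Three quantities are not stated in the documents and are assumed:

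- doses on Day 1, d1: 1 to 3, with 4 shown as the extreme;
- doses on the exit day: 0, which follows from the instructions at a scheduled exit but is an assumption at an unscheduled one;
- whether the dose withheld on a visit morning is made up later that day: either.

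**Completers, exit on Day 85.**

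Q-Q expected: 4 x 85 = 340.
- Low (d1 = 1, withheld doses lost at Visits 3-8): 1 + 77 x 4 + 6 x 3 = 327, and 327/340 = 96.2%.
- High (withheld doses made up): d1 + 83 x 4. With d1 = 3 this is 335/340 = 98.5%; with d1 = 4 it is 336/340 = 98.8%.

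Q-B expected: 4 x 29 + 2 x 56 = 228.
- Low: 1 + 25 x 4 + 2 x 3 + 4 x 1 + 52 x 2 = 215, and 215/228 = 94.3%.
- High: d1 + 27 x 4 + 56 x 2. With d1 = 3 this is 223/228 = 97.8%; with d1 = 4 it is 224/228 = 98.2%.

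**Early exit on Day D, before Visit 5, either regimen.** Expected is 4D. Available, with no exit-day dose and no visit-morning loss, is d1 + 4(D - 2).

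| Exit day | Expected | Available, d1 = 1 to 3 | Compliance |
|---|---|---|---|
| 6 | 24 | 17-19 | 70.8-79.2% |
| 8 | 32 | 25-27 | 78.1-84.4% |
| 10 | 40 | 33-35 | 82.5-87.5% |

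With d1 = 1, (4D - 7)/(4D) < 0.80 gives D < 8.75, so Day 8 is the last exit day affected. If the Visit 3 morning dose is not made up, Day 9 gives 28/36 = 77.8% and Day 10 gives 32/40 = 80.0%, which is not below the cut-off. No one is affected from Day 10 on.

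**Dependence on the assumptions.** With four Day 1 doses, Day 6 gives 20/24 = 83.3%. At an unscheduled exit on Day 4 with 2-3 doses on Day 1 and three on the exit day, the result is 13-14 of 16 = 81-88%. With four on Day 1 and three on the exit day, nobody falls below 80%.

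**Switch day.** The lowest fully adherent Q-B subject leaving on or after Day 29 exits on Day 30: 1 + 25 x 4 + 2 x 3 + 1 = 108 of 4 x 29 + 2 = 118, or 91.5%. The Day 29 over-count lowers Q-B percentages slightly but cannot push anyone below 80%.

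**After dropping the +1.**
- Q-Q completer: 4 x 84 = 336, so the range becomes 327-336 of 336, or 97.3-100%.
- Q-B completer: 4 x 28 + 2 x 56 = 224, so the range becomes 215-224 of 224, or 96.0-100%. Days 1-28 are now charged as QID and Days 29-84 as BID.
- Day 8 exit with d1 = 1: 25/28 = 89.3%, up from 78.1%.
- Day 4 exit with d1 = 1: 9/12 = 75.0%, still low. Day 5: 13/16 = 81.3%.

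**The case against.** The strongest reply is that nothing of consequence rests on this. The compliance category is a descriptive summary on the Safety population. The primary analyses use ITTOD and ITTFSN. The per-protocol definition (SAP 7.2) states no 80% rule and already excludes non-completers. Continuous compliance and a subject listing are produced as well. All of this stands and caps the importance of the point.

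The second reply is that the first-week figures depend on dose counts the documents do not give. That also stands. The withholding instruction covers scheduled visits only, and the Day 1 count is nowhere stated. The exit-day over-count for completers and the Day 29 over-count need neither assumption.

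A reader might infer more than the documents support:

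- *That adherent early leavers in general are labelled non-compliant.* The arithmetic confines this to about the first week.
- *That the Q-B switch day contributes to the label.* It applies only to subjects who reach Visit 5, where adherent subjects are above 91%.
- *That the table is biased against reproxalap.* The formula is the same for active and vehicle within a regimen. A distortion would need more first-week exits in one arm. Protocol Section 2 reports discontinuations for instillation irritation in a trial of 0.1% and 0.5% formulations, mostly the latter. It gives no such rate for 0.25% and no timing, so this is possible but cannot be quantified.
- *That exposure is miscounted as well.* SAP 12.2 uses "Extent of Exposure (days) = [Date of Study Completion/Discontinuation – Date of Visit 2 (Day 1)] + 1", which gives 85 days for a Day 85 exit. Counting both end days is an accepted convention, and without the +1 a subject dosed and discontinued on Day 1 would have zero days of exposure.

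**Conclusion.** The mismatch is real and minor. SAP 12.1 overstates expected doses relative to the protocol's own instructions, by about 1-4% of the total for Q-Q completers and 2-6% for Q-B completers. Under the stated assumptions, some fully adherent subjects leaving by Day 8 or 9 would fall below the 80% cut-off; under the most generous assumptions none would. The number of such subjects cannot be estimated from the documents. The consequence is a compliance table and listing that read slightly low. No efficacy conclusion is affected.

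The zero-compliance rule is a separate edge case. A subject who missed the supervised dose but dosed at home has taken study drug and so belongs to the Safety population (SAP 7.3), yet would be reported as 0% compliant. This should be rare, since supervised instillation is part of Visit 2 for everyone randomized.

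**What to change.** Reconcile SAP 12.1 with the protocol's visit-day instructions:

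1. Q-Q, and Q-B leaving before Visit 5: expected = 4 x (exit date - Visit 2 date).
2. Q-B completing, or leaving at or after Visit 5: expected = 4 x (Visit 5 date - Visit 2 date) + 2 x (exit date - Visit 5 date).
3. Set a minimum of one expected dose for any dosed subject. Otherwise a same-day exit has a denominator of 4 x 0 = 0.
4. Set compliance to 0 only when no dose at all was taken.
5. Footnote exits up to about Day 4, or charge them only the doses available on Day 1, keeping the minimum of one.

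The totals for Day 85 completers then match the protocol's 84 treatment days. Item 5 is needed because the Day 1 over-count remains. The ratio can also err upward in these very short stays: with four doses on Day 1, four on Day 2 and three on an unscheduled Day 3 exit, it is 11/8 = 137.5%, which the SAP would call over-compliant.

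Leave SAP 12.2 as it is. The cost is SAP wording and a few lines of programming, with no new data. The same wording can be carried into the Part 2 SAP, which is to be finalized after the Part 1 database lock.

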7.3 Safety

Safety Population: The safety population includes all randomized subjects who have received at least one dose of study drug. Subjects in the safety population will be analyzed as treated.

8. General Statistical Considerations

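### SAP 12.1 scores as 0% compliant any subject without an in-office dose, and in the compliance table that rule can only reach subjects who did take study drug

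*SAP*

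**What the plan says.** SAP 12.1 defines compliance as doses taken divided by doses expected. For the numerator, "The number of actual doses taken will be recorded from the eCRF". The denominator comes from dates: four doses a day from Visit 2 to exit in the Q-Q arms, and four a day to Visit 5 then two a day to exit in the Q-B arms for subjects who reach Visit 5.

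One exception follows: "For subjects who do not receive a dose of study drug per in office instillation, the number of expected doses will be 0", and for these subjects "compliance will be defined as 0". Anything below 80% is categorised as non-compliant.

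The table's population is also fixed in SAP 12.1: "Dosing compliance (%) will be summarized with continuous descriptive statistics for each treatment arm, using the Safety population". SAP 7.3 defines that population: "The safety population includes all randomized subjects who have received at least one dose of study drug". It does not say where the dose must be taken.

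Protocol 9.3.3 has randomized subjects self-administer a supervised first dose at the site on Visit 2, then dose at home. SAP 12.2 computes exposure from Visit 2 to exit, with no exception for a missed site dose.

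**The concern.** The exception reads as if written for randomized subjects who never took study drug, but its condition is the in-office instillation only. Almost all dosing in this trial takes place at home, so a missed site dose says little about what the subject took over 12 weeks.

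The choice of population makes this more than loose wording. Subjects who never dosed are already outside the Safety population, so the rule cannot touch them in the compliance table. Anyone in that table who meets the condition must have taken drug later, and for that person an expected count of 0 is wrong.

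At stake is the accuracy of a descriptive table and its listing. A nearly fully dosed subject would be shown as 0% and non-compliant, while SAP 12.2 credits the same subject with full exposure. Listing 16.2.5.3 covers both exposure and compliance, so the two values would appear in the same output.

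**Working it through.** The 0 is set by definition, so there is no calculated figure in the plan to reproduce. The check is who can meet the rule, and what the ordinary formulas would give those subjects.

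**Who the rule reaches in the table**

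| Subject | In Safety population (SAP 7.3)? | Meets the zero rule (SAP 12.1)? | Effect in compliance table |
|---|---|---|---|
| Took the site dose | Yes | No | None |
| Never took study drug | No | Yes | None: not in the table |
| Missed the site dose, dosed later | Yes | Yes | Shown as 0%, non-compliant |

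Only the third row is affected.

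**Expected doses by the SAP 12.1 formulas** (nominal days from SAP Table 1: Visit 2 = Day 1, Visit 5 = Day 29, Visit 9 = Day 85)

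- Q-Q: 4 × (85 − 1 + 1) = 340
- Q-B: 4 × (29 − 1 + 1) + 2 × (85 − 29) = 116 + 112 = 228

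**Compliance if only the site dose is missed**

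- Q-Q: 339/340 = 99.7%
- Q-B: 227/228 = 99.6%
- Exposure by SAP 12.2: 85 − 1 + 1 = 85 days

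With exit on Day 82 to 88 and Visit 5 on Day 27 to 31, expected doses run from 328 to 352 (Q-Q) and 218 to 238 (Q-B). Compliance stays between 99.5% and 99.7%.

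**Harsher assumptions** (not in the documents)

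- All Day 1 and Day 85 doses lost: Q-Q (340 − 8)/340 = 97.6%; Q-B (228 − 6)/228 = 97.4%.
- One further dose lost at each of Visits 3 to 8: Q-Q (340 − 14)/340 = 95.9%; Q-B (228 − 12)/228 = 94.7%.

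All of these are far above the 80% cut-off. The rule as written gives 0% in every case.

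**Effect on an arm** (assuming 100 subjects in the summary)

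- Replacing a true 99.7% by 0% lowers the arm mean by 99.7/100, about 1.0 point, whatever the other subjects' values.
- With the other 99 at an assumed 98%: (99 × 98 + 99.7)/100 = 98.02% becomes (99 × 98 + 0)/100 = 97.02%.
- With the others at an assumed 95%, one, two or three such subjects give arm means of 94.05%, 93.10% and 92.15%.
- Each case adds 1/100 = 1 point to the non-compliant category.

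**The case against.** **The in-office record is a fair proxy for having ever dosed.** Protocol 9.3.1 asks for procedures in the listed order, and 9.3.3 places randomization, then supervised instillation, then dispensation. A subject who skips the site dose but goes home with drug has already departed from the protocol, so such cases should be close to nil. This stands as a limit on frequency, for which the documents give no figure. It does not make the rule right in any case where it operates in the table.

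**The rule has a legitimate use.** SAP 8.4 lists data for all randomized subjects unless otherwise specified, so a never-dosed subject needs some value in the compliance listing, and this rule supplies it. An odd 0% would also be visible there beside the accountability and instillation data. This stands too, and the repair keeps that use.

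**A stronger reading is tempting: that the false 0% would remove the subject from the PP, PPOD and PPFSN populations.** Non-compliance with study drug is among the deviation types in SAP 9, and SAP 7.2 excludes significant deviations. The documents do not support the inference. Nothing ties the 80% cut-off to a deviation or to per-protocol membership. SAP 6 and 7.2 have deviations classified and populations settled before the analyses are run. Protocol 9.5 has dosing compliance assessed from collected ampules, with the investigator recording deviations, and a subject dosing fully at home would look compliant on that count.

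**A reader might also infer that missed site doses are expected**, because SAP 9 lists a deviation type for instillation and assignment at site. That category is broad and does not show that the authors anticipated this pattern.

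**Conclusion.** The rule is wrong as written, with low materiality. In the Safety-population summary it can only misstate: every subject it reaches took study drug and is shown as 0%. Where only the site dose was missed, the SAP's own formulas give 99.7% (Q-Q) or 99.6% (Q-B), and the 0% also conflicts with the 85 days of exposure under SAP 12.2.

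The size is about 1 percentage point per case in both the arm mean and the non-compliant category, assuming 100 subjects per arm and near-complete home dosing. Cases should be rare. The effect stays within the compliance table and listing. The primary analyses in ITTOD and ITTFSN do not use compliance, and an effect on the per-protocol populations is not established.

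**What to change.** In SAP 12.1, change the condition so that expected doses and compliance are set to 0 only for randomized subjects who took no dose of study drug at all, at the site or at home, and state that these subjects appear in the listing only. For all other subjects use the date-based expected-dose formula for their arm, so that a missed site dose counts as one missed dose.

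The cost is one sentence in the SAP and one condition in the derivation program. Values for subjects who took the site dose, and for those who never dosed, do not change, and the conflict between 12.1 and 12.2 for subjects who dosed only at home goes away. I see no downside.

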12.2 Treatment Exposure

Extent of treatment exposure for completed or discontinued subjects will be calculated in days using the following:

Extent of Exposure (days) = [Date of Study Completion/Discontinuation – Date of Visit 2 (Day 1)] + 1

Extent of treatment exposure for subjects who were lost to follow-up will be calculated in days using the following:

Extent of Exposure (days) = [Date of Last Recorded Visit – Date of Visit 2 (Day 1)] + 1

Extent of treatment exposure (days) for each subject exposed to study drug will be summarized with continuous descriptive statistics for each treatment arm, using the Safety population.

Subject listings of study drug exposure and dosing compliance will be produced.

13. Efficacy Analyses

